Evaluation Window (Days)	0	0	0	0	0	± 1	± 1	± 1	± 3	± 3	± 3	± 7	± 7	± 7
PK Assessments														
PK Blood Samples ¹¹		X	X		X	X	X		X		X			
Efficacy Assessments														
Tumor Assessment ¹²	X				X (End of every 8 weeks in the first year; and every 12 weeks thereafter)									
Biomarker Exploration														
18F-FES PET/CT ¹³	X								X					
FWD1802 Tablet		X			Continuous Dosing									
Adverse Events	X													
Concomitant Medications and Non-Drug Supportive Interventions	X													

Note: * The tests of hematology, urinalysis, blood biochemistry and coagulation before the first dose administration could be exempted if the tests planned during the screening period were performed within 3 days before the first administration on C0D1. Other examinations may be conducted if deemed clinically necessary by the investigator.

1. Screening assessments are performed within 28 days before C0D1. Screening assessments performed no more than 4 days before C0D1 will qualify as baseline assessments and need not be repeated, unless otherwise specified.
2. The end-of-treatment (EOT) will occur at the earliest day possible within 7 days after the last dose of FWD1802 or the subject decides to withdraw from study treatment for any reason.
3. Safety follow-up (SFU) visit should be performed at 28 ±7 days after the last administration and prior to the initiation of a new anti-tumor therapy. Subjects who discontinue the study due to an unacceptable adverse event should be followed until AE resolves to grade 0-1 or AE is stable. If EOT visit is within the safety follow-up window, no further safety follow-up is required.

4. LTFU (long term follow-up) visit is for survival follow-up. LTFU visit will be performed every 12(\pm 7) weeks after completion of SFU (phone contact is acceptable if the patient cannot return to the site).
5. Physical examination includes examination of whole human body systems (dermatologic, head, eyes, ears, nose, mouth/throat/neck, thyroid, lymph nodes, respiratory, cardiovascular, gastrointestinal, extremities, abdomen, back, musculoskeletal, orientating neurologic, and psychiatric systems).

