In the 28-day repeat-dose toxicity study conducted in beagle dogs: test article-related ophthalmic finding were noted in both sexes at 15 mg/kg/day including bilateral conjunctiva hyperemia and/or ocular discharge. The ocular discharge was also noted in the clinical observations in both sexes at 15 mg/kg/day with higher incidence and the number of animals affected than control group. These signs were recoverable during the recovery phase. Therefore, during clinical trials, the physical examination should be performed regularly to monitor the subject's eye examination..

- Clinical Adverse Effects of FASLODEX® (Fulvestrant)

As a similar-targeted drug, Fulvestrant is an approved SERD for the treatment of endocrine-resistant breast cancers. The most common adverse reactions occurring in $\geq 5\%$ of patients receiving FASLODEX 500 mg were: injection site pain, nausea, bone pain, arthralgia, headache, back pain, fatigue, pain in extremity, hot flash, vomiting, anorexia, asthenia, musculoskeletal pain, cough, dyspnea, and constipation. Increased hepatic enzymes (ALT, AST, ALP) occurred in $>15\%$ of FASLODEX patients and were not dose-dependent.

Comparison of FASLODEX 500 mg and FASLODEX 250 mg (CONFIRM)(FDA, 2021)

The following adverse reactions (Nevens et al.) were calculated based on the safety analysis of CONFIRM comparing the administration of FASLODEX 500 mg intramuscularly once

a month with FASLODEX 250 mg intramuscularly once a month. The most frequently reported adverse reactions in the FASLODEX 500 mg group were injection site pain (11.6% of patients), nausea (9.7% of patients), and bone pain (9.4% of patients); the most frequently reported adverse reactions in the FASLODEX 250 mg group were nausea (13.6% of patients), back pain (10.7% of patients), and injection site pain (9.1% of patients).

Table 5 lists adverse reactions reported with an incidence of 5% or greater, regardless of assessed causality, from CONFIRM.

Table 5 Adverse Reactions in CONFIRM (≥5% in Either Treatment Group)

Adverse Reactions	FASLODEX 500 mg	FASLODEX 250 mg
	N=361 %	N=374 %
Body as a Whole		
Injection Site Pain ¹	12	9
Headache	8	7
Back Pain	8	11
Fatigue	8	6
Pain in Extremity	7	7
Asthenia	6	6
Vascular System		
Hot Flash	7	6
Digestive System		
Nausea	10	14
Vomiting	6	6
Anorexia	6	4
Constipation	5	4
Musculoskeletal System		
Bone Pain	9	8
Arthralgia	8	8
Musculoskeletal Pain	6	3
Respiratory System		
Cough	5	5
Dyspnea	4	5

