4.5 Definition of MTD

- The maximum tolerable dose (MTD) is defined as the highest dose level while the incidence of DLT is less than 33% in the dose escalation study during the DLT evaluation period.
- Six patients are required to establish the MTD. If only 3 patients have been evaluated in the previous dose level below the non-tolerated dose, the cohort should be expanded to 6 patients at the previous dose level below the non-tolerated dose. If DLT is not observed in the additional 3 patients, or 6 patients have been evaluated at the previous

dose level, the MTD will be confirmed at the previous dose level below the non-tolerated dose.

- If MTD is not established at the end of escalation, the maximum safety dose will be defined as the maximum administrated dose (MAD).
- The recommended dose for expansion(s) will be confirmed comprehensively based on the results of safety, tolerability, PK and PD. The RP2D should be a pharmacologically active dose and the dose should be selected by pooling and evaluating all available PK, PD, target engagement, efficacy, safety, and tolerability data to select the appropriate dose. There will need to be at least 6 patients at the recommended dose for expansion level(s) to evaluate the safety, PK, PD and tolerability. If the DLT does not occur during the DLT assessment period, the current highest dose level will not be considered as the basis of dose escalation and may be used as a reference to dose design and safety evaluation of the recommend dose.

Based on the safety data, a higher dose level beyond dose level 9 or an intermediate dose level can be explored as determined by the SMC.

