5.2 Inclusion Criteria

1. Patients must understand and voluntarily sign the Informed Consent Form (ICF).
2. Patients \geq 18 years.
3. Provision of blood sample to test ESR1 mutation status and for other biomarker assessment. In part A/B, the ESR1 mutation status will be tested retrospectively; In part C, only the patients with ESR1 mutation positive is eligible (See Appendix 6).
4. Documented positive oestrogen receptor status of primary or metastatic tumour tissue, according to the local laboratory parameters. HER-2 negative. These laboratory parameters are consistent with accepted diagnostic guidelines such as the American Society of Clinical Oncology (ASCO) / College of American Pathologists (CAP) Clinical Practice Guideline for Pathologists estrogen (ER) and progesterone receptor (PgR) testing in breast cancer ([Allison et al., 2020](#)).
5. Menopausal women according to one of the following criteria:
 - Prior bilateral ovariectomy;
 - Patients \geq 60 years of age;
 - Patients $<$ 60 years of age presenting an amenorrhea of more than 12 months and follicle stimulating hormone (FSH) and plasma estradiol levels within the postmenopausal range as assessed by the local laboratory in the absence of chemotherapy, tamoxifen, tolimifene, or ovarian castration in the past 1 year, and no oral contraceptives, hormone replacement therapy, or gonadotropin-releasing hormone agonist or antagonist;
 - Patients $<$ 60 years of age who are taking either tamoxifen or tolimifene with two consecutive FSH and estradiol levels in the postmenopausal range.
 - Or premenopausal or perimenopausal female subjects but must be willing to receive and maintain an approved luteinizing hormone-releasing hormone(LHRH) agonist during the study treatment period (LHRH agonist treatment initiated 28 days prior to the first study drug treatment); or for males: willing to receive and

maintain an approved LHRH agonist during the study treatment period (LHRH agonist treatment initiated 28 days prior to the first study drug treatment).

6. Previous therapy failed or intolerable, or standard therapy not available:

Part A/C: Previous therapy failed or intolerable, or standard therapy not available.

Part B/C: Patients should have received at least 1 line ET, or received no more than 1-line systematic chemotherapy for advanced/metastatic disease, no more than 1 target therapy.

7. Patients who are HIV positive with CD4+ T-cell counts ≥ 350 cells/uL may be eligible.

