5.3 Exclusion Criteria

1. Documented medical history or ongoing gastrointestinal disease (Including difficulty in swallowing capsules, Crohn's disease, ulcerative colitis, or short bowel syndrome) or other malabsorption that may affect the absorption of oral study drug.
2. Participated in other clinical trials of investigational drugs or investigational devices within 4 weeks before the first medication; or received chemotherapy, targeted therapy, immunotherapy and clinical trial medication and other anti-tumor treatment within 4 weeks, or received radiotherapy, endocrine drugs or Chinese traditional medicines with anti-tumor indications 2 weeks prior to the first dose. Or receive mitomycin and nitrosourea within 6 weeks prior to the first dose.
3. The toxicity of previous anti-tumor treatment has not recovered to grade 0 or 1 (except for alopecia, chemotherapy-induced peripheral neurotoxicity \leq grade 2).
4. Major surgical surgery (except biopsy) or incomplete healing of the surgical incision within 4 weeks prior to the first study drug treatment.
5. Known other malignant tumors within 2 years before enrollment (except for cervical carcinoma insitu, superficial noninvasive bladder tumors, breast ductal carcinoma in situ, prostatic intraepithelial neoplasia without evidence of prostate cancer, or curatively treated Stage I nonmelanoma skin cancer);
6. Subjects with unstable or symptomatic or progressive Central nervous system (CNS) metastasis. Subjects with a history of brain metastases who were clinically stable and who underwent Magnetic resonance imaging (MRI) or Computed tomography (CT) Subjects with CT (if not suitable for MRI) who confirm no CNS disease progression can be enrolled (MRI or CT must be performed at least 4 weeks after the last brain radiotherapy).;
7. Previous history of interstitial lung disease, drug-induced interstitial lung disease, symptomatic interstitial lung disease or any evidence of active pneumonia on chest CT scan within 4 weeks prior to the first study drug treatment;
8. Known to interfere with the test requirements of mental illness or drug abuse disease;
9. History of human immunodeficiency virus HIV infection, or active bacterial or fungal infection requiring systemic treatment within 14 days prior to the first study drug treatment.
10. Presence of active syphilis infection.

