11. Subjects with known active hepatitis B virus (HBV) or hepatitis C virus (HCV) infection with abnormal liver function (Absence of infection was defined as HBsAg negative, HBV DNA negative and HCV antibody negative), except to:
 - Subjects who test positive for HBsAg or HBsAb during the screening period may be enrolled if the PCR test result for HCV-RNA is < 500 IU/ml (2000 copies/mL), but receive antiviral treatment according to the investigator's assessment and undergo PCR for HBV-DNA during the study treatment period;
 - Subject has a positive test for HCV antibody at screening and can be enrolled if the PCR test result for HCV-RNA is negative.
12. History of clinically significant cardiovascular disease, such as:
 - Symptomatic congestive heart failure according to New York Heart Association Grades (NYHA $>$ Grade 2);
 - Severe/unstable angina, new angina within last 3 months;
 - Myocardial ischemia and long-term use of drugs for control; according to NYHA, grade III-IV cardiac insufficiency;
 - Any event of acute myocardial infarction within 6 months before screening;
 - Any grade ≥ 2 supraventricular arrhythmia or ventricular arrhythmia requiring treatment or intervention;
 - Any grade atrial fibrillation, coronary/peripheral artery bypass graft, or cerebrovascular symptoms including transient ischemic attack;
 - QTcF (Fridericia's correction formula used) > 470 ms;
 - ECG < 50 bpm.
13. History of serious allergic reactions to the study drugs or excipients used in the protocol.
14. Women who are pregnant or lactating.
15. Prior use of an oral selective estrogen receptor degrader (SERD).
16. Subjects who use drugs or herbal supplements known to be moderate/strong inhibitors of CYP3A2 weeks prior to the first study drug treatment. Subjects who use drugs or herbal supplements known to be moderate/strong inducers of CYP3A4 weeks prior to the first study drug treatment.
17. Received medications which inhibits the production of stomach acid within 2 weeks or 5 drug half-lives (whichever is longer) prior to the first dose of study drugs.

18. Received medications which inhibits P-gp within 2 weeks or 5 drug half-lives (whichever is longer) prior to the first dose of study drugs.
19. Patients with active or chronic corneal disease, other active eye disease requiring ongoing treatment, or any clinically significant corneal disease for which drug-induced keratopathy cannot be adequately monitored.

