7.3.6 Echocardiogram

Echocardiogram will be performed during the study and left ventricular ejection fraction (LVEF) was recorded.

7.3.7 ^{18}F -FES PET/CT

The patients underwent both ^{18}F -FES and ^{18}F -FDG PET/CT at screening period and C2D8 to monitor the detect in ER target occupation and inhibition. The detection interval between ^{18}F -FES and ^{18}F -FDG PET/CT was within 7 days.

All of the patients were requested to fast for more than 4 h prior to ^{18}F -FES PET/CT scans to eliminate the excretion of ^{18}F -FES from the hepatobiliary system and the gastrointestinal tract, which might interfere with image interpretation in the pelvic cavity.

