7.4.1 Screening Period (Day -28~Day -1) for All Subjects

After signing the ICF, a subject should undergo medical screening to assess whether he/she is eligible to participate in the study according to the inclusion criteria. The screening evaluation will be completed within 28 days prior to the first administration of the investigational drug.

Administrative Procedures:

- Informed Consent
- Inclusion/Exclusion Criteria
- Demographics
- Medical history
- Concurrent diseases

Clinical Procedures/Assessments:

- Weight
- Body height
- Physical examination
- vital signs

- ECOG Score
- 12-lead ECG
- Echocardiogram

Laboratory tests:

- Blood Chemistry
- Hematology
- Coagulation
- Urinalysis
- Virology: HBV, HCV, and HIV
- Pregnancy
- COVID-19

Efficacy Assessments:

- Tumor Assessment

Biomarker Exploration:

- ¹⁸F-FES PET/CT15

Other:

- Adverse events and concomitant medication;

The information above should be obtained from the source file. For test values outside the normal range (outliers), the investigator will assess whether to repeat the test.

The investigator will review patient's medical history at the time of screening period. The history includes all current active diseases and any other conditions deemed clinically significant by the investigator. The date of last prior anticancer therapy(s) and treatment response must be recorded. Pre-enrollment imaging data can be collected for the investigator's reference. A complete medication history within 28 days prior to the first administration of the study drug should be reported.

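### In Parts A and C the baseline FES-PET is not tied to any interval free of ER-binding drugs, so prior tamoxifen or fulvestrant can lower the baseline and understate ER inhibition

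*Protocol*

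**What the plan says.** **Endocrine drugs.** Protocol 5.3, exclusion 2, bars "endocrine drugs or Chinese traditional medicines with anti-tumor indications 2 weeks prior to the first dose". Exclusion 15 is limited to "Prior use of an oral selective estrogen receptor degrader (SERD"), so prior injected fulvestrant does not exclude a patient. One route to menopausal status in 5.2, criterion 5, covers women under 60 "who are taking either tamoxifen or tolimifene with two consecutive FSH and estradiol levels in the postmenopausal range".

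**The scan.** Section 7.3.7 asks for "PET/CT at screening period and C2D8 to monitor the detect in ER target occupation and inhibition". It adds a fasting rule and a limit on the gap between the FES and FDG scans, but says nothing about drugs that act on the receptor. Section 7.4.1 lists the FES-PET among the screening procedures and states: "The screening evaluation will be completed within 28 days prior to the first administration of the investigational drug". Tables 1 and 3 mark a scan at screening and one in Cycle 2, with no repeat before the first dose. Table 2 (Part B) marks only the Cycle 2 scan.

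**Two passages that bear on timing.** Section 6.7 prohibits other antitumor treatment during a study period that it describes as including screening. Footnote 1 of Table 1 reads: "Screening assessments performed no more than 4 days before C0D1 will qualify as baseline assessments and need not be repeated, unless otherwise specified". The same footnote in Tables 2 and 3 gives 7 days.

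**Use of the result.** Section 3.4 plans to correlate ER inhibition on FES-PET with efficacy. Section 10.6 explores how dose or exposure relates to biomarkers. Section 4.5 selects the RP2D by "evaluating all available PK, PD, target engagement, efficacy, safety, and tolerability data".

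**The concern.** FES-PET is the trial's reading of how much ER remains available. By the protocol's own background (1.1), SERMs compete for ER binding, fulvestrant leads to ER degradation, and FWD1802 binds with an affinity close to that of fulvestrant. A patient scanned while another ER-binding drug is still acting has a baseline that is already lowered. The further fall after FWD1802 then looks smaller than it would from a clean baseline.

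The distortion depends on the previous drug and the day of the scan, not on the FWD1802 dose. In Part A cohorts of at most 6 patients, a chance difference in prior therapy could pass for a difference in target engagement between doses. A clean baseline cannot be obtained once dosing has started, so scan timing has to be settled in the protocol rather than in the analysis.

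**Working it through.** The plan gives no figure for the FES-PET measure, so there is nothing to reproduce. Two checks apply.

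**1. Day count**

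- Screening window (7.4.1): D-28 to D-1, 28 days.
- Endocrine bar (exclusion 2): the last 14 of those days, D-14 to D-1.
- Days on which the scan is allowed but the bar has not begun: D-28 to D-15, which is 28 - 14 = 14 days.

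For fulvestrant, the last 14 days are not clear either. Section 1.4.1 describes its dosing as "FASLODEX 250 mg intramuscularly once a month", with the 500 mg dose also monthly. Taking a month as 28 days (an assumption), an injection on D-15 is compatible with exclusion 2 and is only 14 days old on D-1. A full interval before a D-1 scan would require the last injection on or before D-29. This compares dosing intervals only. The protocol gives no half-life or duration of occupancy for fulvestrant or tamoxifen.

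**2. Direction and possible size of the bias**

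Assume that inhibition is read as the relative fall in FES uptake from baseline; the protocol does not define it. Let T be the true inhibition against an unblocked baseline and b the share of ER already blocked at the baseline scan. On treatment, uptake is (1 - T) of the unblocked level. The measured baseline is (1 - b) of it. Then

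measured inhibition = 1 - (1 - T)/(1 - b).

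For any b above 0 this is less than T, so the direction is understatement. With T = 80%:

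- b = 0: 1 - 0.20/1.00 = 80%
- b = 30%: 1 - 0.20/0.70 = 71%
- b = 60%: 1 - 0.20/0.40 = 50%

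Other assumed values of T show the range:

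| True T | b = 10% | b = 25% | b = 50% |
|---|---|---|---|
| 60% | 56% | 47% | 20% |
| 75% | 72% | 67% | 50% |
| 90% | 89% | 87% | 80% |

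With T = 80% throughout and one patient 60% pre-blocked, the mean of a cohort of 3 reads (80 + 80 + 50)/3 = 70%. The mean of a cohort of 6 reads (5 × 80 + 50)/6 = 75%. T and b are assumptions; the documents supply neither.

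**The case against.** **Section 6.7 already bars antitumor drugs in screening.** Read literally it does, and exclusion 2 cannot then be taken as permission to stay on a SERM or fulvestrant until D-15. This stands as a conflict between the two sections. It does not remove the problem, because a drug could be stopped just before an early screening scan without breaching 6.7.

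**Footnote 1 already confines baseline to the last 4 or 7 days.** If it governs the PET, the scan falls after the 2-week bar and only fulvestrant carry-over remains. But the footnote decides which screening assessments must be repeated, and no pre-dose repeat PET is scheduled. Its application to the scan is unclear.

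**Criterion 5.** A reader might infer that it admits women taking tamoxifen at screening. It does not say that. It is a test of menopausal status, read alongside exclusion 2 and 6.7. It shows only that recent tamoxifen use is foreseen.

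**Carry-over is not quantified.** This stands. A monthly schedule describes dosing, not how long the receptor stays blocked.

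**The measure is exploratory.** This also stands. No FES threshold or formal comparison between cohorts is planned, and target engagement is one of several inputs to a judgement. A reader might conclude that dose cohorts cannot be compared at all. The documents support only that the comparison is confounded.

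**Conclusion.** The point holds for Parts A and C. The only pre-treatment FES-PET may be taken on any of 28 days, 14 of them before the endocrine bar begins. No passage requires an interval free of ER-binding drug before it, and prior fulvestrant is allowed. A pre-blocked baseline understates ER inhibition. The direction follows if inhibition is read as a relative fall from baseline, but the size cannot be fixed from the documents, and the 71% and 50% readings are illustrations.

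Two wider readings are not supported. The first extends the point to Part B: Table 2 shows no screening PET there, although 7.3.7 and 7.4.1 call for one, so that is a discrepancy to resolve first. The second extends it to all endocrine therapy: the argument concerns drugs that act on the receptor, and nothing here shows the same for aromatase inhibitors.

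What is affected is the exploratory work in 3.4 and 10.6 and one input to the RP2D in 4.5. This is a worthwhile, inexpensive improvement, not a flaw that undermines the trial.

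**What to change.** Leave the washout rule unchanged.

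1. In 7.3.7 and Tables 1 and 3, schedule the baseline FES-PET only once the exclusion 2 interval since the last ER-binding endocrine drug has elapsed.
2. State whether footnote 1 applies to the PET.
3. Reconcile exclusion 2 with 6.7, and Table 2 with 7.3.7 and 7.4.1.
4. Record the name and last date of any ER-binding drug. Section 7.4.1 already requires the date of the last prior anticancer therapy, so this adds little.
5. Report FES change with and without patients whose last fulvestrant dose was less than one monthly interval before the baseline scan. This is needed because step 1 alone does not remove fulvestrant carry-over.

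The cost is a narrower window for booking the scan and one sensitivity table. In cohorts of this size that table will be small and descriptive only.

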Statistical Methods	
Descriptive analysis (summary statistics) will be used to describe the safety and efficacy endpoints.
 
Safety Analysis:
 
Incidence and severity of adverse events according to the NCI-CTCAE (V5.0) will be summarized and displayed in number/percentage. The exposure extent to the study drug will be displayed.. 
Efficacy Analysis:
 
The ORR and its exact 95% Clopper-Pearson confidence interval will be calculated. The CBR, DCR will also be calculated similarly. All of the time-to-event data (PFS, DOR, OS) will be estimated using Kaplan-Meier method, and the median along with two-sided 95% CI will be displayed (use the Greenwood's formula for estimation of standard errors). 
Pharmacokinetic analysis:
 
A descriptive analysis of the plasma concentration and derived PK parameters of FWD1802 and its metabolite (if possible) will be conducted by dose level. Plasma concentration patient profiles versus time and mean concentration versus time will be displayed.

Table 1 Schedule of Events in Part A Dose Escalation

Items	Screening ¹	Single dose			Multiple dose							Follow-up		
		4 days			Cycle 1 28days				Cycle 2		≥Cycle3	EOT ₂	SFU ₃	LTFU ⁴
Visit Day	D-28~ D-1	D 1	D2~ D4		D1	D8	D1 5	D2 2	D1	D15	D 1			
Evaluation Window (Days)	0	0	0	0	0	± 1	± 1	± 1	± 3	± 3	± 3	± 7	± 7	± 7
Administrative Procedures														
Informed Consent	X													
Inclusion/Exclusion Criteria	X													
Demographics	X													
Medical history	X													
Concurrent diseases	X													
Clinical Procedures/Assessments														
Weight	X	X			X	X	X	X	X	X	X	X		
Body height	X	X			X	X	X	X	X	X	X	X		
Physical examination ⁵	X	X	X		X	X	X	X	X	X	X	X		
Vital signs ⁶	X	X	X		X	X	X	X	X	X	X	X		
ECOG Score	X	X	X		X	X	X	X	X	X	X	X		
12-lead ECG ⁷	X	X			X	X	X	X	X	X	X	X		
Echocardiogram	X				X						X (Every 3weeks)			
Laboratory Assessments														
Blood Chemistry	X	X*			X	X	X	X	X	X	X	X		
Hematology	X	X*			X	X	X	X	X	X	X	X		
Coagulation	X	X*			X	X	X	X	X	X	X	X		
Urinalysis	X	X*			X	X	X	X	X	X	X	X		
Virology: HBV, HCV, and HIV ⁸	X													
Pregnancy ⁹	X													
COVID-19 ¹⁰	X													

Items	Screening ¹	Single dose			Multiple dose							Follow-up		
		4 days			Cycle 1 28days				Cycle 2		≥Cycle3	EOT ₂	SFU ₃	LTFU ⁴
Visit Day	D-28~ D-1	D 1	D2~ D4		D1	D8	D1 5	D2 2	D1	D15	D 1			

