6. Vital signs include temperature, pulse, breathing and blood pressure. On C0D1 and C1D1, the vital signs will be measured at pre-morning dose(s), and 0.5 h, 2 h, 4 h, 8 h, 12 h and 24 h after the morning dose(s). On C0D3, C0D4, C1D8, C1D15, C1D22, C2D1, C2D15, (C3~Cn) D1, the vital signs will be measured at pre-morning dose(s). Other examinations may be conducted if deemed clinically necessary by the investigator.
7. 12-lead ECG will be performed three times at Screening, 30 min, 20 min and 10 min pre-dose and 0.5 h, 1 h, 1.5 h, 2 h, 3 h, 4 h, 5 h, 6 h, 8 h, 12 h and 24 h post-dose on C0D1 and C1D1, and the spacing between each ECG examination will be at least 1 min. On C1D8, C1D15, C1D22, C2D1, C2D15, (C3~Cn) D1, the 12-lead ECG will be measured at pre-morning dose(s) and 2 h after the morning dose(s). Meanwhile, 12-lead ECG will be performed on prematurely withdrawn. If QTcF > 450 ms (male) or > 470 ms (female), 3 consecutive ECGs should be collected to calculate the mean QTcF value.
8. Human immunodeficiency virus antibody, hepatitis B surface antigen, hepatitis B core antibody, hepatitis C virus antibody, and Treponema pallidum antibody. period and may optionally be done at additional time points depending on investigator discretion.
9. Only applicable to women of childbearing age; Subjects must have a negative blood pregnancy test during the screening period. Pregnancy tests will be performed anytime during the course of the study, as per investigator's discretion. Serum or urine tests are acceptable based on the site's standard clinical practice, if a urine pregnancy test is positive, it must be confirmed by a serum pregnancy test.
10. Infectious disease screening includes polymerase chain reaction for SARS-CoV-2;
11. Blood will be collected for PK analysis of the FWD1802 Tablet and/or its metabolites (if any), details please refer to 7.5.1 PK Samples.
12. Tumor assessment: All patients will undergo MRI, chest, abdomen, pelvis and bone examination at baseline period, and subsequent imageological examination included the chest, abdomen, pelvis, and other metastatic sites, if any. The preferred

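### Exclusion 11 admits hepatitis B-positive patients on an HCV-RNA limit where HBV-DNA was evidently meant, so HBV viral load has no ceiling at entry

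*Protocol*

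**What the plan says.** Criterion 11 in Protocol 5.3 excludes patients with known active HBV or HCV "infection with abnormal liver function". A bracket in the same sentence adds: "Absence of infection was defined as HBsAg negative, HBV DNA negative and HCV antibody negative". Two exceptions follow.

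- **First exception.** It covers patients who are HBsAg- or HBsAb-positive at screening. They "may be enrolled if the PCR test result for HCV-RNA is" below "500 IU/ml (2000 copies/mL"). They must also receive antiviral treatment as the investigator judges and "undergo PCR for HBV-DNA during the study treatment period".
- **Second exception.** It covers patients positive for HCV antibody. Such a patient "can be enrolled if the PCR test result for HCV-RNA is negative".

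The synopsis carries the same two exceptions, with HCV-RNA in the first.

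Footnote 8 to Tables 1, 2 and 3 lists the virology tests: HIV antibody, hepatitis B surface antigen, hepatitis B core antibody, HCV antibody and Treponema pallidum antibody. Further virology "may optionally be done at additional time points depending on investigator discretion". Part of that footnote is visibly missing.

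**The concern.** A viral-load condition attached to hepatitis B carriers should measure hepatitis B virus. This one measures hepatitis C virus, so it does not limit what it was written to limit.

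Two things are at stake in a first-in-human study (Protocol 4.1). The first is patient safety: the one clause meant to cap HBV viral load at entry does not do so. The second is attribution of liver events. Protocol 4.6 counts ALT/AST elevations and Hy's law as dose-limiting toxicities. The Hy's law definition requires that no other cause of liver injury exists, and other events are discounted only when the alternative cause is beyond doubt. Under Protocol 4.4 one DLT in the first three patients expands a cohort and two stop escalation. A liver event in a patient with uncontrolled hepatitis B could therefore be hard to attribute, and it could move the dose decision. This does not suggest that FWD1802 reactivates hepatitis B; the protocol gives no data on that.

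**Working it through.** No power, alpha or event count is involved, so the check sets the parts of the protocol side by side.

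**1. Which marker was meant?** Four features of criterion 11 point to HBV-DNA:

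- The first exception is triggered by HBsAg or HBsAb, both hepatitis B markers.
- The same bullet requires HBV-DNA PCR on treatment.
- The parent sentence uses HBV DNA, not HCV-RNA, in defining absence of infection.
- HCV-RNA already has a rule in the second exception, and a stricter one (negative rather than below 500 IU/ml).

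**2. What does the printed text do?** The last column replaces HCV-RNA with HBV-DNA at the printed threshold.

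| Patient | First exception as printed | Second exception | First exception corrected |
|---|---|---|---|
| HBsAg positive, HCV negative, any HBV-DNA level | Met | Not relevant | Met only if HBV-DNA < 500 IU/ml |
| HBsAg positive and HCV antibody positive, HCV-RNA detectable but < 500 IU/ml | Met | Not met | Decided by HBV-DNA; HCV-RNA is left to the second exception |

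The first row is the main consequence: an HCV-negative patient always satisfies an HCV-RNA ceiling, so the condition filters nobody on HBV viral load. The second row shows the two bullets giving different answers on the same HCV-RNA result.

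**3. Does another part of the protocol supply the missing ceiling?**

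- *Parent sentence of criterion 11.* The bracket defines absence of infection. It sets no viral-load limit for patients admitted by exception.
- *Inclusion 11 (5.2).* It limits bilirubin to 1.5 × ULN and ALT/AST to 3 × ULN, or 5 × ULN with liver metastasis. These are liver-function limits. A patient with raised transaminases inside them can still be HBsAg-positive at any viral load.
- *Schedules.* The "Blood Chemistry" row in Tables 1 and 2 covers C1 D1, D8, D15 and D22, C2 D1 and D15, then D1 of each cycle. Table 3 has D1 of each cycle only. This detects injury after entry.
- *Sections 1.4.2 and 4.7.3, and exclusion 20.* These provide extra laboratory tests if needed, treatment suspension for adverse events, and investigator discretion. None names HBV-DNA.

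**4. Threshold as printed.** 2000 copies/mL ÷ 500 IU/ml = 4 copies per IU. The protocol does not say whether this conversion was set for an HBV-DNA assay, so the sponsor should confirm it with the marker.

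**5. Two related ambiguities.**

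- The liver-function phrase in the parent sentence can be read as a gate, so that only patients with abnormal liver tests are excluded. The bracketed definition has no liver-function element. The protocol does not say whether a corrected limit would reach HBsAg-positive patients with normal liver tests.
- Criterion 11 requires HBV-DNA PCR on treatment, but Tables 1 to 3 name no such test and no visit for it.

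**The case against.** The strongest reply accepts the wrong marker and disputes how much follows from it.

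- **The slip is obvious.** A site reading the whole criterion would probably notice it. That may be so, but eligibility is applied as written. A site that enforces an HBV-DNA limit refuses a patient the text admits; a site that follows the text enrols without a limit. Only the sponsor can settle the marker and the threshold.
- **The bullets do not truly conflict.** Each can be read as lifting the exclusion for its own virus, and the clash arises only in doubly positive patients. This is largely right: the clash is a symptom of the same slip and goes away with the correction. It is not a second defect.
- **The correction alone may not cap everyone.** If abnormal liver function is a gate, HBsAg-positive patients with normal liver tests never need the exception. This stands, and it is why the fix includes a clarifying clause.
- **Other safeguards exist.** Besides those already listed, there are the hepatic DLT rules, the INR entry limit, grade-based dose reduction, and chemistry at C0D1 in Part A and at end of treatment. They reduce the risk. None sets an HBV-DNA limit.
- **The schedule point is weak.** Footnote 8 is broken, and Table 10 leaves infectious-disease screening as an open list. That is fair, so the schedule request is secondary. Footnote 8 also lists surface antigen and core antibody but not HBsAb, so any schedule entry must say which markers trigger it.

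**Conclusion.** The concern holds and the criterion must be corrected. The wrong marker appears twice, in the synopsis and in 5.3. As written, the first exception sets no HBV-DNA ceiling; corrected at the printed threshold, it would set 500 IU/ml.

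That HBV-DNA was meant is near certain from criterion 11 itself. The reach of the safety consequence is less certain: it covers at least HBsAg-positive patients with abnormal liver function inside the inclusion limits, and whether it extends to those with normal liver tests depends on the unresolved parent sentence. The number affected among the 99 planned patients cannot be estimated from the protocol. Sample size and error rates are unaffected.

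**What to change.** 1. In the first exception of criterion 11, in both the synopsis and 5.3, replace HCV-RNA with HBV-DNA. The sponsor should confirm the 500 IU/ml threshold and its copies/mL equivalent.
2. Add one clause stating whether the HBV-DNA limit applies to every HBsAg-positive patient or only to those with abnormal liver function.
3. As a supporting clarification, name HBV-DNA PCR in footnote 8 for patients positive on stated HBV markers, and give the on-treatment PCR that criterion 11 already requires a visit in Tables 1, 2 and 3.

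Items 1 and 2 cost one marker name in two places and one clause. Item 3 adds a footnote edit and one schedule entry in three tables, for HBV-marker-positive patients only.
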